We employed the G* Power version 3.1.9.7 software program to calculate the sample size based on the specified parameters.: a total sample size of approximately ..., an effect size of 0.5, α error probability of 0.05, Power (1- β error probability) of 0.95, two groups, three measurements, and a correlation among repeated measures of 0.5. The program recommended a minimum sample size of 140 nurses. However, the researchers decided to recruit 150 nurses for both the control group and the study group.

[figure not shown]
To be eligible for the study, nurses had to be.....

As shown in figure (1), each randomly selected nurses were screened to identify the student who met the predetermined inclusion criteria. Three students refused to participate and were excluded due to lack of inclusion criteria. A comprehensive list of the rest, containing the names and relevant data of all students was compiled. The participants were assigned to either the control or study group using a computer-generated randomization list (....each). This random assignment ensured fairness and minimized bias.nurses were withdrawn from either the control or intervention group

Table 1: Stratified random sample using proportion allocation technique.

Academic Level	Strata according to the department	The Expected population size of each stratum	Proportionate sample size in each stratum
1			
2			
3			
4			

Total	Size of the entire population=	Total sample size = 150
--------------	---------------------------------------	--

Intervention (n=62)
Completed post-intervention assessment=60
Lost or dropped out in second post-test = 2

Control (n=61)
Completed post-intervention assessment=60
Lost or dropped out in second post-test = 1
(Not included in the analyse)

Analyzed (n=60)

Analyzed (n=60)

CONSORT analysis of nurses' enrollment and recruitment process

Follow up

Analysis

Tools of data collection: A questionnaire sheet was used to collect data for this study and composed of five parts:

Part (1): This covers staff nurses ' demographic information such as age, department, education level, years of experience, and previous training in job crafting.

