head nurses of the departments were briefed on the upcoming research. This step was included as this may aid in the effectiveness of the intervention as they may stimulate and motivate the nurses to part-take in the intervention with motivation and enthusiasm. The pre-test forms have been given to nurses to determine their training needs regarding job crafting and job crafting behavior among Nurses. The data were gathered during morning and afternoon shifts for four days / week. The time each staff nurse needed to complete each sheet varied from 25 to 30 minutes. The learning needs of nurses were established based on pre-test results. Accordingly, the program's goals have been set out and the content developed.

Implementation phase: ((please insert in table with sessions name, objective, time, steps).

The training program designed for this study was implemented through twelve sessions, from which three theory and nine practical sessions were held in a room at the worksite. The sessions were conducted outside of working hours in the hospital. These sessions lasted 21 hours; 3 theory hours (one hour for each theoretical session); and 9 practical sessions (two hours for each practical session). Having the whole number of nurses at the same time was difficult, so the nurses were classified into five groups each group consisting of about 16 nurses. All sessions were repeated to the five main groups until 80 nurses completed the entire 21-hours instruction period.

The program includes three main parts;

the first theoretical part covers knowledge of the job crafting, job crafting theory, Job Demands–Resources model, definition work environment, combine work environment and JD- R model. Then, based on examples from structured interviews conducted before the program, examples of job crafting are provided, as well as examples of a work analysis. Success stories of past job crafting behaviors of staff nurses were shared and discussed. This was helpful to reflect on the current work performance, and then made their own individual job crafting plans.

The second practical part was included to guide the employees on how to craft their daily activities and to give them suggestions on craft-able work-related activities as 1- increasing job Resources e.g. ask feedback, ask support, ask for help from colleagues or your leaders if you need help, participate committees, look for trainings, invest in

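### Nurses are sampled by department, but no department strata are named for assignment to arms and no department term for the analysis: a minor loss of balance and precision that is cheap to recover

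*Protocol*

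**What the plan says.** - **Selection.** In the Sample size section, Table 1 is titled as a "Stratified random sample using proportion allocation technique", with a column headed "Strata according to the department" and a total of 150. The stratum rows carry no entries.
- **Assignment.** After screening, "A comprehensive list of the rest, containing the names and relevant data of all students was compiled". Then: "The participants were assigned to either the control or study group using a computer-generated randomization list". The number per arm is left blank, and no strata, blocks or department are mentioned.
- **Data.** Part (1) of the questionnaire records "age, department, education level, years of experience, and previous training in job crafting".
- **Analysis.** The Statistical design section names descriptive statistics, a paired t-test and Pearson correlation. Department appears in none of them.
- **Elsewhere.** Section 3.4 (Randomization and Blinding), at the end of the document, belongs to a description of 94 nurses at a hospital in another governorate. It cannot fill the gap, and it names no strata either.

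**The concern.** Sampling strata and randomisation strata do different jobs. The first fix how many nurses come from each department in total; the second fix how those nurses are split between arms. The protocol describes only the first. Under a simple 1:1 list, one arm can by chance hold more nurses from a given department.

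The outcomes are self-reported job crafting, work meaningfulness, attitude to change, and task and adaptive performance. It is plausible, though the protocol neither states nor quantifies it, that such scores vary between departments of an emergency hospital. If they do, uneven department mix adds noise to a between-arm difference, and a reader of the baseline table may see a visible imbalance on the factor that the plan itself chose for sampling. Precision and face validity are at stake; the validity of the randomisation is not.

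**Working it through.** **Inputs from the protocol.** Total 150 (Table 1), so 75 per arm if split equally; 62 and 61 nurses in the flow chart, 60 analysed in each arm; effect size 0.5, correlation among repeated measures 0.5, two groups, three measurements, alpha 0.05, power 0.95 (Sample size).

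**Assumptions.** The protocol gives neither the number nor the size of departments, nor the share of outcome variance that they explain (ρ). I take 4 to 8 equal departments (or one holding 25% of nurses) and ρ = 5 to 15%, with 20% as an extreme.

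**1. The plan's own figure.** Repeated-measures ANOVA, between factors, λ = f²·N·m/(1+(m−1)r), with 0.5 read as a standardised difference (f = 0.25), m = 3 and r = 0.5. This gives N = 142, and power 0.949 at N = 140, against the stated 140. Read as f, 0.5 gives 38 (between factors) or 14 (within factors or interaction). The standardised-difference reading comes closest, so I use it as the scale below, although the protocol does not state the metric.

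**2. Imbalance in one department.** SD of the difference in share = √(p(1−p)·2/n), with p = 0.25:
- n = 75: √(0.25·0.75·2/75) = 0.071, 95% range about ±14 points.
- n = 60: √(0.25·0.75·2/60) = 0.079, 95% range about ±15 points.

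**3. Largest gap over all departments** (simulated simple 1:1 allocation, 4 to 8 departments):

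| N | Median | 95th percentile | Chance of a gap over 10 points |
|---|---|---|---|
| 150 | 8–9 points | 13–17 points | 36–47% |
| 123 | 10–11 points | 15–19 points | 52–61% |

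**4. Effect on a mean difference at one time point.** With ρ = 0.10 and 75 per arm, the SD of the part due to department mix is √(0.10·2/75) = 0.052 outcome SDs. The whole standard error is √(2/75) = 0.163. The ratio of variances is 0.052²/0.163² ≈ 0.10, which is the assumed ρ: this component is already inside the ordinary standard error and does not add to it.

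**5. Gain from adjusting, without baseline.** Reduction in standard error = 1 − √(1−ρ): 2.5% at ρ = 0.05, 5.1% at 0.10, 7.8% at 0.15.

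**6. Gain once baseline is used.** Take stable department effects and a baseline–outcome correlation of 0.5. With baseline alone the residual variance is 1 − 0.5² = 0.75. Adding department, the within-department correlation is r_w = (0.5−ρ)/(1−ρ) and the residual variance is (1−ρ)(1−r_w²).
- ρ = 0.05: r_w = 0.474, variance 0.737, reduction 1 − √(0.737/0.75) = 0.9%.
- ρ = 0.10: r_w = 0.444, variance 0.722, reduction 1.9%.
- ρ = 0.15: r_w = 0.412, variance 0.706, reduction 3.0%.

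**7. Type I error and power** (simulation: 6 departments, N = 150, between-arm test at one time point, difference 0.5 SD, no baseline):

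| ρ | Type I error, simple list, unadjusted | Power, simple list, unadjusted | Power, simple list, adjusted | Power, stratified and adjusted |
|---|---|---|---|---|
| 5% | 5.2% | 0.866 | 0.870 | 0.883 |
| 10% | 4.9% | 0.864 | 0.883 | 0.883 |
| 20% | 4.5% | 0.869 | 0.913 | 0.928 |

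Each power figure rests on 3,000 runs, so its Monte Carlo standard error is about √(0.87·0.13/3000) = 0.006; differences of a point or so are within noise.

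**The case against.** The case for leaving the plan alone has real weight.

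- **Simple randomisation is valid.** Stratified sampling does not oblige anyone to stratify assignment. This stands. A reader might infer that the arms are biased by department; steps 4 and 7 show that they are not.
- **The list may have been stratified.** The protocol does not say that it was not. This stands: the text supports only that no strata are named. Since the method of assignment belongs in the protocol, the sponsor should still say which it was.
- **Adjustment may sit in an analysis plan not shown.** Covariates are commonly left there, so the absence of a department term is not a fault by itself. The case for naming one rests on the small gain it brings.
- **The only comparison test named is paired.** A reader might infer that department differences inflate the error of that test. They do not: a stable department effect cancels in each nurse's change score. The loss arises only in a between-arm comparison, or if departments change differently over time. Hypotheses 3 and 4 concern the experimental group and need a between-arm comparison; that none is named is a separate and larger matter.
- **Department is not ignored.** It is a questionnaire item, and nurses from all departments were interviewed to tailor the program. It is unused only in assignment and in the stated analysis.
- **The evidence for department effects is thin.** The protocol reports that "head nurses of the departments were briefed on the upcoming research". A reader might infer separate or differing briefings for each department, but nothing there says so.

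What remains is a modest gain at almost no cost, using a variable that the plan already treats as important.

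**Conclusion.** The point holds as a minor one. The plan stratifies selection by department, names no strata for assignment and no department term for analysis, and so leaves chance differences in department mix between the arms. The consequence is lost precision in a between-arm comparison: about 2.5 to 8% of the standard error if departments explain 5 to 15% of outcome variance, falling to roughly 1 to 3% once a baseline score correlated 0.5 with the outcome is included. Type I error is unaffected.

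A 95% range of about ±0.10 SD for the department component (1.96 × 0.052) may tempt a reader to call the disturbance a fifth of the planned effect. That compares an extreme with an effect whose metric is unstated, and it isolates a piece of an overall ±0.32 (1.96 × 0.163) for which the test already allows. The documents do not support that reading.

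All sizes depend on the assumed department shares and variance explained. Fewer or more alike departments would make the point smaller still.

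**What to change.** **If assignment is already done**, which the Field work dates (March to August 2023, in a document dated 8-1-2024) and the completed flow chart suggest:
1. Keep the list as generated.
2. State whether it was stratified by department.
3. Report the department mix by arm.
4. Include department, with the baseline score, as a prespecified term in the between-arm comparison that hypotheses 3 and 4 need.

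**If assignment is still to come:** complete the department rows of Table 1, randomise 1:1 in permuted blocks within those departments, and use the same adjusted comparison.

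**Cost.** No extra nurses, visits or questionnaire items. Adjustment spends a few degrees of freedom (five for six departments, out of 148 for a two-group comparison of 150 nurses). Very small departments may have to be pooled, by a rule fixed before outcomes are examined by arm.

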relationships, and clean your desk to work more efficiently. 2- increasing challenging job demands e.g. volunteer work for a committee, communication about emotional/serious issues to patients and families, offer to be responsible for making the nursing schedule in a certain month, share your head nurse in writing certain documents, and stay informed about current and recent research.3- decreasing hindering job demands e.g. simplify tasks, work more efficient, let go perfectionism, say 'no', make clear appointments, checking emails only at certain times during the day and make use of relationships. The staff nurses were then asked to conduct a personal work analysis, guided by questions in their personal action plan. They were also provided with a homework papers for a job crafting exercise. Each staff nurse reviewed his/her own job crafting plan individually (20 min); the nurses then shared their reflections as a group (30 min), discussed what job crafting would be feasible and sustainable to practice (35 min), and, finally, made a modified job crafting plan (35 min). Thereby aiming to increase awareness for the utility of job crafting in their work environment.

The third and last part

consisted of setting personal goals. These goals were aimed at the three job crafting dimensions and had to be SMART5. Complementary, the participants had to formulate actions to attain their personal goals. Each staff nurse had one week to attain his or her goal with respect to the corresponding job craft dimension of that week. The researchers used different teaching approaches to attract the attention of nurses and to inspire them to participate, such as seminars, group discussion and brainstorm. The teaching media included: power point, white blackboard and a copy of the program which covered theoretical and practical information about job crafting, Job Demands–Resources model, combine work environment and JD- R model. All data were collected using a self-report questionnaire at baseline, post-intervention, and three-month follow-up.

Evaluation phase: The impact of the educational program was measured during this phase; it was carried out immediately after the program was introduced and followed up after 3 months of implementation using the same method formats used before the program was implemented.

Administrative and ethical considerations:

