Before the research started, ethical approval was given by the Scientific Research Ethics Committee at the Faculty of Nursing-Zagazig University (NO: 056). Participants were

explained the study objective and protocol, and only those who provided informed consent were included. Voluntary participation, autonomy, and confidentiality of the information gathered were confirmed.

Statistical design:

All data were collected, tabulated, and statistically analyzed using version 20.0 of the Social Science Statistical Package (SPSS), quantitative data were expressed as mean \pm SD and range, and qualitative data were expressed as absolute frequencies (number) & relative frequencies (percentage). Paired t-test was used to compare normally distributed variables between two dependent groups. P.

Pearson correlation coefficient has been determined to determine the relationship between different variables of the sample,(+) sign indicates direct correlation and-) (sign indicates reverse correlation, even values close to 1 indicate strong correlation and values close to 0 indicate weak correlation. All testing was two-sided. P-value < 0.05 was deemed statistically significant (S), and p-value < 0.001 was considered highly statistically significant (HS), and p-value ≥ 0.05 was considered statistically insignificant (NS).

References

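### The flow figure removes nurses lost at the second post-test, so a randomised trial is analysed on completers; the effect is small on the printed counts, but true attrition cannot be established

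*Protocol*

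**What the plan says.** The flow figure under Sample size in the Protocol is the only place that says who is analysed.

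- Intervention arm: 62 nurses, "Lost or dropped out in second post-test = 2", 60 analysed.
- Control arm: 61 nurses, "Lost or dropped out in second post-test = 1", 60 analysed.
- Losses carry the label "Not included in the analyse". It is printed under the control box, but the analysed count of 60 in both arms shows that it applies to both.

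On timing, the Implementation phase of Field work states: "All data were collected using a self-report questionnaire at baseline, post-intervention, and three-month follow-up". The only comparison test named under Statistical design is: "Paired t-test was used to compare normally distributed variables between two dependent groups". No section states an analysis of all randomised nurses or a method for missing scores.

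Other counts appear elsewhere. Sample size gives a minimum of 140 and a plan to recruit 150, and leaves the number assigned to each arm blank. The Implementation phase speaks of 80 trained nurses.

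**The concern.** Random assignment makes the arms comparable at entry. Removing nurses for something that happened after assignment weakens that, because those who stay may differ from those who leave, and differently in each arm. All outcomes are self-reported, and the sessions were held outside working hours, so a link between staying and motivation is plausible, though the Protocol has no data on it.

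Information is also lost. With three assessments, a nurse absent from the last one has at least a baseline record and may have a first post-test score. The figure discards both.

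The named test does not force this. A paired comparison of baseline with the first post-test could include any nurse who has both scores. The exclusion is a rule that the figure sets.

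**Working it through.** **Inputs (flow figure).** Intervention 62, lost 2; control 61, lost 1; analysed 60 and 60.

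**Step 1: reproduce the analysed set.** 62 − 2 = 60 and 61 − 1 = 60, total 120. This matches exactly, so the analysed nurses are those not lost at the second post-test. Loss is 2/62 = 3.2% against 1/61 = 1.6%; overall 3/123 = 2.4%.

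**Step 2: possible shift in the between-arm difference.** The Protocol gives no outcomes for the lost nurses, so their distance from completers is an assumption, c SD. Dropping them moves an arm's mean by (lost/n) × c. If they deviate in the same direction in both arms, the difference moves by (2/62 − 1/61) × c. If they deviate in opposite directions, it moves by (2/62 + 1/61) × c.

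| Assumed c (SD) | Same direction | Opposite directions |
|---|---|---|
| 0.5 | 0.008 | 0.024 |
| 1 | 0.016 | 0.049 |
| 2 | 0.032 | 0.097 |

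For scale, the standard error of a simple difference with 60 per arm is √(1/60 + 1/60) = 0.183 SD. At c = 1 even the opposite-direction shift is about a quarter of that (0.049/0.183 = 0.27).

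**Step 3: precision.** Inputs from Sample size: effect 0.5, alpha 0.05, power 0.95, two groups, three measurements, correlation 0.5. The Protocol does not say what metric the 0.5 is in. Read as a standardised mean difference (f = 0.25) with a between-group repeated-measures test, the noncentrality is N × f² × m / (1 + (m − 1)ρ) = N × 0.0625 × 3/2. This requires 142 nurses, close to the printed 140. On that reading power is 0.914 at 120, 0.921 at 123, 0.949 at 140 and 0.961 at 150. Restoring the three nurses gains less than one percentage point, and that is an upper limit because it treats their data as complete.

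**Step 4: are the printed counts this trial's counts?** They cannot all be right.

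- The flow figure holds 62 + 61 = 123 nurses; the plan was to recruit 150.
- Training is described for five groups of about 16, and 5 × 16 = 80, yet the intervention arm in the figure has 62.
- The pilot of 8 is called 10% of the sample, which implies 8/0.10 = 80, not 123 or 150.
- The number randomised per arm is blank.

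If 150 were randomised, 120 analysed would mean 30/150 = 20% excluded, against the 2.4% that the figure shows. No shift in SD is calculated for that case, because the Protocol gives neither the split of those 30 between arms nor anything about their scores.

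**The case against.** The strongest reply is that three nurses in 123 cannot matter much, and that the model and the missing-data method normally belong in a statistical analysis plan, which is not at hand. The first part stands for the printed counts. The second does not answer the point: the Protocol does not leave the question open, but states that lost nurses are excluded.

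It is also fair to say that the lost nurses may have no first post-test score. The same boxes give 60 per arm as having done the assessment after the intervention, and elsewhere the Protocol uses that term for the first post-test. The figure is ambiguous here. A nurse with only a baseline score would add almost nothing to the estimated effect under any model. A mixed model also removes bias only if scores are missing at random. Both limits are accepted.

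A reader might infer three stronger claims, none of which the Protocol supports.

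- *That the trained group is defined by completion.* The sentence "All sessions were repeated to the five main groups until 80 nurses completed the entire 21-hours instruction period" invites this. But it follows "the nurses were classified into five groups each group consisting of about 16 nurses", and 80 is simply five times 16. It describes delivery, not an analysis set, and nothing says that nurses who did not finish were removed.
- *That selection acts in the trained arm only and so favours the program.* The sections on this trial do not describe what the control arm attended. The one description of control sessions (section 3.6) sits in text about a different trial at a Port Said hospital.
- *That attrition is about 16%.* The 15.95% in section 3.2 belongs to that same other trial, where losses were nearly balanced: 47 to 39 and 47 to 40, or 8 and 7.

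**Conclusion.** The point holds on the flow figure alone: the Protocol sets a completers-only analysis for a randomised comparison and discards whatever the lost nurses contributed. On the printed counts it is a minor flaw: 2.4% lost, a shift of about 0.016 to 0.05 SD if the lost nurses differ by 1 SD, and under one point of power. Those sizes rest on an assumed 1 SD gap and on the counts of 62 and 61 being this trial's own.

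The second condition is doubtful. With the number randomised blank and counts of 123, 150 and 80 unreconciled, true attrition is unknown and could be as high as 20% if 150 were randomised. The documents do not show that it is, and they do not show the direction of any bias.

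**What to change.** 1. In the flow figure, replace the exclusion label with a rule that all randomised nurses are analysed in their assigned arm regardless of attendance.
2. State that the analysis is a likelihood-based repeated-measures model using baseline and every available later score, and that it is valid under missing at random. Report completers only as a sensitivity analysis.
3. Fill in the number randomised per arm and show in the figure how many nurses gave scores at each of the three assessments. That also settles whether the lost nurses have a first post-test score.
4. Reconcile the 62 and 61 in the figure with the 150 to be recruited and the 80 trained.

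The cost is slightly more analysis work and possibly a slightly smaller estimate. No extra nurses are needed. Field work is described as already carried out in 2023, so the change can be made on the data in hand.

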To investigate the effectiveness of job crafting intervention program on job crafting behavior, work meaningfulness, change attitude, adaptive and task performance among nurses at Zagazig university hospitals.

Research hypothesis:

1. After program intervention, nurses will demonstrate an increase in job crafting behavior (increasing job Resources, increasing challenging job demands, and decreasing hindering job demands).
2. Nurses participating in the intervention program will report higher levels of work meaningfulness.
3. The experimental group will demonstrate an increase in positive work attitude and decrease in negative work attitude

4. The experimental group will experience a higher adaptive performance and perform higher levels of task performance.
5. An increase in job crafting behavior is related to and predicts work meaningfulness, change attitude, adaptive and task performance among nurses

Subjects and Methods:

Research design:

The study described in ClinicalTrials.gov with the identifier NCT.....utilized a randomized control trials research design.

Administrative & Ethical Steps:

We obtained official written authorization from the Zagazig university hospitals in order to carry out our research, following the approval of ethical considerations. Formal consent and authorization for the study were also acquired from the Research Ethics Committee within the Faculty of Nursing at Zagazig University, Egypt (IRB:). Patients were duly informed about the study's objectives, and we obtained their informed written consent. They were informed of their right to decline participation, with the assurance that their decision would not impact their care. Moreover, patients were assured that they had the option to withdraw from the study at any point, even after initiation, with the assurance of maintaining their privacy and confidentiality.

Study setting :

This study was conducted at the Zagazig University Emergency Hospital, which provides a wide spectrum of health services at El Sharkia Governorate in Egypt. This hospital receives emergency cases and injuries 3 days/week from Zagazig City and other near areas, giving care for about 7.5 million people, according to the hospital most recent statistical data. The hospital is occupied with (185) beds.

Subjects:

Include staff nurses working in different departments of Zagazig University Emergency Hospital.

Sample size :

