Part (2): Job Crafting questionnaire was developed by Tims, et al. (2012). It consisted of 13 items with three subscales [1] seeking resources included 6 items e.g.(I ask others for feedback on my job Performance), [2] seeking challenges included three items, e.g.(I ask for more tasks if I finish my work), and reducing demands by using 4 items e.g.(I try to ensure that my work is emotionally less intense) . The *questionnaire* was measured on five-point ranging scale from (1) “Never” to (5) “Always”. The total score of this tool ranged from 13-65. Scores \geq [] indicated a higher perception level of job crafting behavior, scores [] indicated a moderate level, while scores [] indicated a low perception level (please reference to level). (please reference if tools used with nurse and previous reliability and consistency). The reliability of the tool was measured by Cronbach alpha coefficient and it was ranged from .87 to .92

Part (3): Work And Meaning Inventory(WAM I)

The scale was developed by Steger et al.(2012), to reflect weekly work meaningfulness by using the 10-items. The WAMI consists of three facets: positive meaning 4 items e.g. (I understand how my work contributes to my life's meaning this week), meaning making 3 items e.g. (This week, I viewed my work as contributing to my personal growth), and greater good motivations 3 items e.g.(This week, I knew my work made a positive difference in the world). All items were scored on a five-point Likert scale ranging from 1 (absolutely untrue) to 5 (absolutely true). The total score of this tool ranged from 10-50. Scores \geq [] indicated a higher perception level of work meaningfulness, scores [] indicated a moderate level, while scores [] indicated a low perception level(please reference to level). (please reference if tools used with nurse and previous reliability and consistency). . The reliability of the tool was measured by Cronbach alpha coefficient, it ranged from .60 to .81 (M = .71).

Part (4): Change attitude scale: This dependent variable was measured using 15 items from Dunham et.al (1989), to measure the affective, cognitive and behavioral dimensions of attitude towards change. It includes two subcategories; positive attitude

towards change with 7 items e.g.(I am happy at the prospect of this change), and negative attitude towards change 8 items e.g. (I find it difficult to accept new things).

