All statements were rated on a scale Likert that went from 1 (strongly disagree) to 5 (strongly agree). *Scoring system: The total score of this tool ranged from 15-75.*

The scores were categorized into highly openness to change (positive attitude) (participants who scored $> 75\%$ on attitude based questions), and (resistance) unfavorable negative attitude (participants who scored $\leq 75\%$ on attitude based questions). (please reference to level). (please reference if tools used with nurse and previous reliability and consistency). Cronbach's alphas was ($\alpha=.859$).

Part (5): Task, Contextual and Adaptive performance scales: was used for measuring task and Adaptive performance; task performance was measured by a scale developed by Williams and Anderson (1991). Seven items on task performance were measured e.g. (Fulfills responsibilities specified in job description") They were measured on a five-point ranging scale from (1) "Strongly disagree" to (5) "Strongly agree". The total score of this tool ranged from 7-35. Scores $\geq []$ indicated a high levels of task performance, scores [] indicated a moderate level, while scores [] indicated a low perception level (please reference to level). (please reference if tools used with nurse and previous reliability and consistency). . Cronbach alpha was $\alpha=.770$.

Adaptive performance: was measured on a five item scale. This originated from the preferences of the Elkerliek hospital. A sample item for adaptive performance include: "I use the screening in the quality chart to predict risk on delirium"; "I use the checklist in the care chart";"I use prevention actions and treatment interventions in my daily job". The scale ranges from (1) "Never" to 5"Extremely often". The total score of this tool ranged from 5-25. Scores $\geq []$ indicated a high levels of adaptive performance, scores [] indicated a moderate level, while scores [] indicated a low perception level adaptive performance(please reference to level). (please reference if tools used with nurse and previous reliability and consistency). . Cronbach alpha was $\alpha=.909$.

Content validity and reliability:

After the instrument was translated into Arabic, data were collected using a self-administered questionnaire. A jury of experts (5 professors & 7 assistant professors)

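### The only change attitude score defined sums opposed items without a stated recode, and even a correctly reversed total cannot separate the two parts of hypothesis 3

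*Protocol*

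**What the plan says.** Part (4) under the protocol's tools of data collection describes a 15-item change attitude scale. "It includes two subcategories; positive attitude" towards change has 7 items, and the other subcategory is described as "negative attitude towards change 8 items e.g. (I find it difficult to accept new things". The response format is the same for both sets: "All statements were rated on a scale Likert that went from 1 (strongly disagree) to 5 (strongly agree". The scoring system then gives one range, "The total score of this tool ranged from 15-75", and one two-way split of it, introduced by the words "The scores were categorized into highly openness to change (positive attitude": above 75% counts as open to change, and 75% or below counts as resistant. No score or range is given for either subcategory, no recode of the negative items is stated, and the percentage has no stated base.

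Hypothesis 3 has two parts: "The experimental group will demonstrate an increase in positive work attitude and decrease in negative work attitude". It speaks of work attitude, whereas the scale measures attitude towards change. As this is the only attitude scale collected, it is taken here to be the one meant. Hypothesis 5 also uses the construct: "An increase in job crafting behavior is related to and predicts work meaningfulness, change attitude, adaptive and task performance among nurses". The statistical design section names a paired t-test and a Pearson correlation but does not say which attitude score enters either.

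**The concern.** Agreement means opposite things in the two item sets. A nurse who becomes more favourable should move up on the 7 positive items and down on the 8 negative ones. If responses are simply added, these movements offset each other, and because there is one more negative item, an equal favourable shift per item lowers the total slightly.

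Reversing the negative items cures the direction but not the mismatch with hypothesis 3. That hypothesis makes two separate predictions, and one total cannot say which of them was met. A significant rise could be reported as support for the whole hypothesis when only one part moved. A total summed without recoding would also distort any hypothesis 5 correlation that used it.

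**Working it through.** **Inputs.** 7 positive items, 8 negative items, responses 1 to 5, total 15-75 and cut above 75%, all from Part (4); the two predictions from hypothesis 3. The response patterns and shifts below are illustrations, not trial data.

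**The protocol's own range.** 15 × 1 = 15 and 15 × 5 = 75, so the stated range is right. It is the same with or without reversal, so it does not settle the coding. The subcategory ranges follow: 7 × 1 to 7 × 5 = 7-35, and 8 × 1 to 8 × 5 = 8-40.

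**Two codings.** Let p be the mean response to the positive items and n the mean response to the negative items.

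- Literal total: 7p + 8n
- Reversed total: 7p + 8(6 − n)

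| Response pattern | p | n | Literal | Reversed |
|---|---|---|---|---|
| Most open | 5 | 1 | 35 + 8 = 43 | 35 + 40 = 75 |
| Most resistant | 1 | 5 | 7 + 40 = 47 | 7 + 8 = 15 |
| Strongly agrees with everything | 5 | 5 | 35 + 40 = 75 | 35 + 8 = 43 |
| Neutral throughout | 3 | 3 | 21 + 24 = 45 | 21 + 24 = 45 |
| Mildly open | 4 | 2 | 28 + 16 = 44 | 28 + 32 = 60 |

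**The cut.** 75% of the maximum is 0.75 × 75 = 56.25. 75% of the range is 15 + 0.75 × 60 = 60. On the literal total, 43 and 47 both fall below either cut, so the most open and the most resistant nurse share the resistant class, while 75 is classed as open. A nurse who answers 2 or less on every negative item can reach at most 35 + 16 = 51 and can never be classed as open.

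**Change over time, literal coding.** The literal total changes by 7Δp + 8Δn and the reversed total by 7Δp − 8Δn.

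| Δp | Δn | Literal | Reversed |
|---|---|---|---|
| +0.5 | −0.5 | 3.5 − 4.0 = −0.5 | 3.5 + 4.0 = +7.5 |
| +0.5 | −0.25 | 3.5 − 2.0 = +1.5 | 3.5 + 2.0 = +5.5 |
| +0.25 | −0.5 | 1.75 − 4.0 = −2.25 | 1.75 + 4.0 = +5.75 |

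Every row is a favourable change. The literal total shrinks it or turns its sign.

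**Separating the two predictions, reversed coding.** A rise of 7 results from Δp = 1.0 with Δn = 0 (7 × 1.0 = 7). It results equally from Δp = 0 with Δn = −0.875 (8 × 0.875 = 7). In the first case negative attitude has not fallen, in the second positive attitude has not risen, and the total is identical.

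**Base of the 75%.** Totals of 57, 58, 59 and 60 lie above 56.25 but not above 60, so they change class with the reading. The mildly open nurse, with a reversed total of 60, is at 60/75 = 80% of the maximum (open) but at (60 − 15)/60 = 75.0% of the range (resistant).

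**The case against.** The best defence is that the protocol is brief rather than wrong. The item counts and range agree with each other, recoding is routine, and assigning scores to hypotheses is often left to an analysis plan, which is not at hand here. The two named subcategories match the two parts of hypothesis 3 and could serve it directly. The job crafting scale is handled alike: three subscales are named and only a total range is given. The class labels make sense only if the negative items are reversed. Finally, the 75% class feeds no named test, so its base affects a descriptive table at most.

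Much of this stands. A reader might infer that the trial will analyse an unreversed total, or that hypothesis 3 will be tested on the total or on the 75% class. The documents support none of these: no passage assigns any score to that hypothesis, and the labels point towards reversal.

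What does not stand is that this is mere silence. The protocol sets out a scoring rule, and followed as written that rule ranks the most open nurse below the most resistant. The only score it defines does not fit its own two-part hypothesis under either coding.

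**Conclusion.** The point holds and should be fixed. Two results carry it. As written, the total has no consistent direction: 43 for the most open nurse against 47 for the most resistant, and −0.5 instead of +7.5 for a favourable half-point shift on every item. Correctly reversed, it still cannot distinguish a rise in positive attitude from a fall in negative attitude.

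The first result bites only if the negative items are in fact summed without recoding, which is the less likely intent. The second needs no assumption about coding, but does harm only if the total is what tests hypothesis 3. Both assume that hypothesis 3 refers to this scale despite its different wording. The protocol gives no score distribution, so the number of nurses who would change class between the two readings of 75% is unknown; that part is a secondary reporting matter.

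**What to change.** In the scoring system of Part (4), define two continuous scores: positive attitude (7 items, 7-35) and negative attitude (8 items, 8-40). Under hypothesis 3, state that each part is tested on its own score and that the full hypothesis is claimed only if both parts hold. State that the 8 negative items are recoded as 6 minus the response before any total, 75% class or hypothesis 5 correlation uses them. For reporting, add whether 75% is of the maximum (above 56.25) or of the range (above 60).

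The cost is a few sentences and one recode of answers already collected. Hypothesis 3 then needs two tests instead of one. Requiring both to succeed calls for no split of the significance level, but it is harder to pass than a single test.
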